Appendix 6. Tumor Lysis prophylaxis

Risk categories for development of tumor lysis syndrome (TLS)

Based on review of all currently available data, three risk categories for developing TLS were defined including the size of the enlarged lymph nodes and the absolute lymphocyte count (ALC). In addition, the creatinine-clearance (CrCl) of the patient needs to be taken into account by the investigator (see below).

The following risk categories were defined:

	Low Risk	Medium Risk	High Risk				
Lymph Nodes	All measurable	Presence of any	A single	Any single			
	lymph nodes with	single measurable	measurable	measurable			
	the largest	lymph node with the	lymph node with	lymph node with			
	diameter <5 cm by	largest diameter	the largest	the largest			
	radiographic	≥5 cm and <10 cm	diameter ≥5 cm	diameter			
	assessment	by radiologic	by radiologic	≥10 cm by			
		assessment	assessment.	radiologic			
				assessment			
	AND	OR	AND				
Absolute							
lymphocyte	< 25 × 10 ⁹ /L	≥ 25 × 10 ⁹ /L	≥ 25 × 10 ⁹ /L				
Count (ALC)							

All patients enrolled in the trial will be assessed at screening and categorized based on their tumor burden, as described above. Patients can be restaged into a lower TLS risk group at any time according to their ALC.

Please note: Patients with **CrCl** < **80 ml/min** should be monitored very closely for signs of TLS, especially if they are in the intermediate or high risk TLS risk category (lymph node \geq 5 and/or ALC $\geq 25 \times 10^9$ /L).

Patients with CrCl 30-50 ml/min should be handled as high risk patients.

Initial dosing and monitoring

Low and medium risk patients

- Administration of an oral uric acid reducer (such as allopurinol 300 mg/day) beginning at least 24 hours prior to first dose and continued until at least 28 days after last dose escalation.
- Laboratory assessment of clinical chemistries (see under 'laboratory monitoring') and
 assessment of vital signs are required pre-dose, 6-8- and 24-hours post-dose at first dose of
 20 mg and 50 mg. Pre-dose and 24 hours post-dose are required at subsequent ramp-up
 doses. The pre-dose laboratory samples are to be reviewed prior to dosing and should not
 demonstrate any clinically significant abnormalities prior to the first dose of venetoclax, or the
 patient should receive additional prophylactic treatment and hydration prior to the initiation of
 dosing.
- Post-dose Monitor clinical chemistries (see under 'laboratory assessments') for evidence of TLS at 6 – 8 hours after the first dose of 20 mg and 50 mg. The 6-8-hour post-dose laboratory values must be reviewed prior to a patient leaving the clinic and electrolyte abnormalities should be corrected promptly
- Serum chemistries must be re-assessed before administering the second dose of each rampup (i.e., at 24 hours).
- Any patient who, at any dose, develops clinically significant electrolyte abnormalities must have his or her subsequent venetoclax dose withheld until the electrolyte abnormalities resolve.
- Patients who develop electrolyte abnormalities should undergo aggressive management and further monitoring as outlined below (see under 'further actions')'.
- Oral hydration consisting of fluid intake of >2 L/day should be maintained during the whole ramp-up period of venetoclax.

High risk patients

- Administration of an oral uric acid reducer (such as allopurinol 300 mg/day) beginning at least 24 hours prior to first dose and continued until at least 28 days after last dose escalation.
- Laboratory assessment of clinical chemistries (see under 'laboratory monitoring') and assessment of vital signs are required pre-dose, 6-8 and 24 hours post-dose on the first day of each dose level, The pre-dose laboratory samples are to be reviewed prior to dosing and should not demonstrate any clinically significant abnormalities prior to the first dose of venetoclax, or the patient should receive additional prophylactic treatment and hydration prior to the initiation of dosing.
- Post-dose: Monitor clinical chemistries (see under 'laboratory assessments') for evidence of TLS at 6 – 8 hours at first dose of each dose level. The 6-8-hour post-dose laboratory values must be reviewed prior to a patient leaving the clinic and electrolyte abnormalities should be corrected promptly
- Serum chemistries must be re-assessed before administering the second dose of each rampup (i.e., at 24 hours).
- Any patient who, at any dose, develops clinically significant electrolyte abnormalities must have his or her subsequent venetoclax dose withheld until the electrolyte abnormalities resolve.
- Patients who develop electrolyte abnormalities should undergo aggressive management and further monitoring as outlined below (see under 'further actions')'.
- Oral hydration consisting of fluid intake of >2 L/day should be maintained during the whole ramp-up period of venetoclax.

The following table summarizes the safety precautions for mitigation of TLS depending on different risk categories:

Recommended TLS Prophylaxis Based on Tumor Burden from Clinical Trial.

Data (consider all patient co-morbidities before final determination of prophylaxis and monitoring schedule).

	Tumor Burden	Proph	nylaxis	Blood Chemistry Monitoring ^{c,d}		
		Hydrationa	Anti- hyperuricemics	Setting and Frequency of Assessments		
Low	All LN <5 cm AND ALC <25 x10 ⁹ /L	Oral (1.5-2 L)	Allopurinol ^b	Outpatient 1. Pre-dose, 6 to 8 hours, 24 hours at first dose of 20 mg and 50 mg 2. Pre-dose and 24 hours at at subsequent ramp- up doses		
Medium	Any LN 5 cm to <10 cm OR ALC ≥25 x10 ⁹ /L	Oral (1.5-2 L) and consider additional intravenous	Allopurinol	Outpatient 3. Pre-dose, 6 to 8 hours, 24 hours at first dose of 20 mg and 50 mg 4. Pre-dose and 24 hours at subsequent ramp-up doses 5. Consider hospitalization for subjects with CrCl <80mL/min at first dose of 20 mg and 50 mg; see below for monitoring in hospital		
High	Any LN ≥10 cm OR ALC ≥25 x10 ⁹ /L AND any LN ≥5 cm	Oral (1.5-2 L) and intravenous (150-200 mL/hr as tolerated)	Allopurinol; rasburicase is recommended if baseline uric acid is elevated (ALLOPURINOL SHOULD NOT BE GIVEN AT SAME DAY AS RASBURICASE)	In hospital (recommended) at first dose of 20 mg and 50 mg 6. Pre-dose, 6 to 8, and 24 hours Outpatient at subsequent ramp-up doses 7. Pre-dose, 6 to 8 hours, 24 hours		

ALC = absolute lymphocyte count; LN = lymph node.

- a Administer intravenous hydration for any patient who cannot tolerate oral hydration.
- b Start allopurinol or xanthine oxidase inhibitor at least 1 day prior to initiation of venetoclax.
- c Evaluate blood chemistries (potassium, uric acid, phosphorus, calcium, and creatinine); review in real time
- For subjects at low/medium risk of TLS, monitor blood chemistries pre-dose and 24 hours at each subsequent ramp-up dose. For subjects at high risk of TLS, monitor blood chemistries pre-dose, at 6-8 hours and at 24 hours at each dose level.

Hydration: Ensure adequate hydration prior to initiating therapy with venetoclax and throughout the ramp-up phase, especially the first day of each ramp-up dose. Administer intravenous (IV) fluids as indicated based on overall risk of TLS or for those who cannot maintain adequate oral hydration.

Anti-hyperuricemic agents: Administer uric acid reducing agents (e.g., allopurinol). Start at least 1 day prior to initiation of venetoclax; consider continuing through the ramp-up phase.

Laboratory Assessments:

Pre-dose (within 24 hours prior to ramp-up dose):

- Sodium, potassium, calcium, phosphate, chloride
- uric acid, urea, total bilirubin, serum creatinine
- LDH
- complete blood count (CBC), including hemoglobin, platelets and white blood cell count with differentials
- liver enzymes (AST, ALT, alkaline phosphatase)

_

Assess blood chemistries mentioned above prior to initiating venetoclax to evaluate kidney function and correct pre-existing hyperuricemia, hyperkalemia, hyperphosphatemia, or hypocalcemia to normal levels. Reassess blood chemistries before starting each subsequent ramp-up dose of venetoclax.

Post-dose: For subjects at low or medium risk of TLS, monitor blood chemistries at 6-8 hours and at 24 hours after initiating venetoclax at the 20 mg and 50 mg doses. For subjects at high risk of TLS, monitor blood chemistries in the hospital at 4, 8, 12 and 24 hours after initiating venetoclax at the 20 mg and 50 mg doses; subsequent ramp-up doses can be administered in the outpatient setting with monitoring of blood chemistries at 6-8 hours and at 24 hours after initiating venetoclax. Electrolyte abnormalities should be corrected promptly. The next dose of venetoclax should not be administered until the 24-hour blood chemistry results have been evaluated.

Hospitalization:

Based on physician assessment, some patients, especially those at greater risk of TLS, may require hospitalization on the day of the first dose of venetoclax for more intensive prophylaxis and monitoring during the first 24 hours. Hospitalization should be considered for subsequent dose increases based on reassessment of risk.

Scoring of tumor lysis syndrome and further actions

The below listed criteria defined by Cairo and Bishop should be used to diagnose a laboratory or clinical TLS.

Laboratory Tumor Lysis Syndrome (LTLS):

Laboratory Parameter	Laboratory Result
Uric Acid	≥ 476 µmol/L (≥ 8.0 mg/dL) or 25% increase from baseline
Potassium	≥ 6.0 mmol/L (≥ 6.0 mEq/L) or 25% increase from baseline
Phosphorous	≥1.45 mmol/L (≥ 4.5 mg/dL) or 25 % increase from baseline
Calcium	≤ 1.75 mmol/L (≤ 7.0 mg/dL) or 25% decrease from baseline

Laboratory tumor lysis syndrome (LTLS) is defined as either a 25% change or level above or below normal, as defined above, **for any two or more serum values** of uric acid, potassium, phosphate, and calcium within 3 days before or 7 days after the initiation of chemotherapy. This assessment assumes that a patient has or will receive adequate hydration (± alkalinization) and a hypouricaemic agent(s) (Cairo, 2004).

Clinical Tumor Lysis Syndrome (CTLS):

Clinical tumor lysis syndrome (CTLS) assumes the laboratory evidence of metabolic changes and significant clinical toxicity that requires clinical intervention.

The presence of LTLS and one or more of the following criteria:
Creatinine: ≥ 1.5 ULN *
Cardiac arrhythmia / sudden death*
Seizure*

(*Not directly or probably attributable to a therapeutic agent (e.g. rise in creatinine after amphotericin administration)). (Cairo, 2004)

Cairo-Bishop Tumor Lysis Syndrome Grading

ino bishop rumor Lysis dynarome Ordanig								
#	Grade 0	Grade 1	Grade 2	Grade 3	Grade 4	Grade 5		
LTLS	-*	+	+	+	+	+		
Creatinine#	≤ 1.5 x ULN	1.5 x ULN	> 1.5-3.0 x ULN	> 3.0-6.0 x ULN	> 6.0 x ULN	Death\$		
Cardiac arrythmia#	None	Intervention not indicated	Nonurgent medical intervention indicated	Symptomatic and incompletely controlled medically or controlled with	Life-threatening (e.g., arrhythmia associated with CHF.	Death ^{\$}		
				device (e.g., defibrillator)	hypotension, syncope, shock			
Seizure#	None	-	One brief, generalized seizure; seizures(s) well controlled by anticonsulvants; or infrequent focal motor seizures not interfering with ADL	Seizures in which consciousness is altered; poorly controlled seizure disorder, with breakthrough generalized seizure despite medical intervention	Seizures of any kind which are prolonged, repetitive, or difficult to control (e.g., status epilepticus, intractable epilepsy)	Death ^{\$}		

CTLS requires one or more clinical manifestations along with criteria for LTLS Maximal CTLS manifestation (renal, cardiac, neuro) defines the grade

- * No LTLS
- * Not directly or probably related to a therapeutic agent
- \$ Attributive probably or definitely to CTLS

Further actions need to be taken in case of:

- potassium increase by ≥0.5mmol/l from baseline and/or any potassium value >5.0 mmol/l
- phosphorus increase of >0.5 mg/dl 0.16 mmol/l and >4.5 mg/dl 1,45 mmol/l
- any other significant laboratory change, especially electrolyte imbalances

These actions should be according to the institutional practice and include but are not limited to:

- discontinuation of administration of venetoclax, no further dosage should be taken until resolution
- hospitalization for more aggressive monitoring (especially regular laboratory assessments, telemetry/ECG monitoring, observation for signs/symptoms of TLS (e.g. fever, chills, tachycardia, nausea/vomiting, diarrhea, sweating, hypotension, muscle aches, weakness, paresthesias, mental status changes, confusion, and seizures)
- administration of intravenous fluids at a rate of ≥1 ml/kg/h (≥50 ml/hr., target 150 to 200 ml/hr.; as clinically appropriate)
- in case the diagnosis of TLS is established, further measures, such as urine alkalization with intravenous sodium bicarbonate or administration of rasburicase as per institutional practice should be considered
- consultation of nephrology (or acute dialysis service) to ensure emergency dialysis is available

Please note: A rapidly rising serum potassium level is a medical emergency.

Reassessment of risk category

Patients classified as high risk for developing TLS who presented at screening with BOTH an ALC≥ 25 x 10⁹/L AND a measurable lymph node with the largest diameter ≥ 5 cm by radiologic assessment may have their TLS risk category reassessed.

Prior to dose increases above 50 mg of venetoclax, patients may have a reassessment of their disease status based on their most recent ALC. Based on those results, one of the following two options may be implemented:

- If the patient's ALC decreases to < 25 x 10⁹/L, patients may be re-categorized as medium risk and follow the management guidelines for the medium-risk category for the subsequent increases in dose during the dose ramp-up period.
- If the patient's ALC remains ≥ 25 × 10⁹/L, they will remain in the high-risk category and continue to follow management guidelines for high-risk patients for subsequent dose increases of venetoclax during the dose ramp-up period.

Reassessment of the patient's risk category can occur prior to each subsequent dose increase.

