Pregnancy test ⁵		Х	X ⁶				X ⁷	X ⁷	X ⁷					
ECOG Performance	X	Χ												
ECG		Х												
(PET)-CT scan		Х								Χ				Χ
Lab tests														
Hematology		Х	Х	Х	Χ	X	Χ	Χ	X	Χ		X	Х	Χ
Blood chemistry		Х	X	Х	Χ	Χ	Χ	Χ	X	Χ		X	X	Х
Additional chemistry		Х								Х		X	X	Х
Virology		Х								Х		Х	Х	Χ

¹ No laboratory testing except for standard of care based on the discretion of the local investigator, this visit is for informed consent to assemble data for assessment by the CLL-TIM algorithm

² Max 42 days from screening to randomization, however FISH and TP53 mutational results are accepted up to six months prior to randomization, max 14 days from randomization to cycle 1 day 1 (C1D1)

³ Only for treatment arm.

⁴ TLŚ chemistry the day before, 6 h after ramp up dose of venetoclax and the day after (24 h) before next dose of venetoclax

⁵ Only applies for women of child bearing potential

⁶ A negative pregnancy test is required for all women of child bearing potential within 7 days before start of study treatment

⁷ Only applies for the women of child bearing potential in the treatment arm

Biobank blood	Х	X ³	X ³	Χ	Х	Х	Χ	Х	Х	Χ
Central lab										
IGHV, FISH, Recur	Χ									Х
Flow-MRD	Χ					Х	Χ	Х	Х	Χ
PK samples					X8					
Bone marrow										
Biopsy and aspirate	Х			Χ	Х	Х	Χ			Χ
Aspirate biobank	Х						Χ			X ⁹
Microbiome samples										
Feces, saliva, skin, buccal swabs	X					Х	Х			

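### Appendix 6 gives two different timings for lowering the TLS risk category of patients who are high risk through ALC plus a node of 5 to <10 cm

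*Protocol*

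**What the plan says.** Appendix 6 of the protocol sorts patients into three TLS risk categories by node size and ALC. High risk is reached in two ways: a node of at least 5 cm together with ALC ≥25 × 10⁹/L, or any node of at least 10 cm whatever the ALC. Medium risk is a node of 5 to <10 cm or ALC ≥25 × 10⁹/L. Patients with creatinine clearance (CrCl) of 30–50 mL/min are handled as high risk.

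Below that table stands a rule for all enrolled patients: "Patients can be restaged into a lower TLS risk group at any time according to their ALC". It carries no dose limit, exception or cross-reference.

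The last part of the same appendix, Reassessment of risk category, deals with patients who were high risk at screening through ALC and node together: "Prior to dose increases above 50 mg of venetoclax, patients may have a reassessment of their disease status based on their most recent ALC". If ALC has fallen below 25 × 10⁹/L they may be managed as medium risk for later increases; if not, they stay high risk. It closes by adding that reassessment of the patient's "risk category can occur prior to each subsequent dose increase".

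The prophylaxis table in Appendix 6 ties precautions to the category. The high-risk row reads "In hospital (recommended) at first dose of 20 mg and 50 mg", with intravenous fluid at 150–200 mL/hr as tolerated on top of oral fluid. The medium-risk row is outpatient, with additional intravenous fluid only to be considered, and adds "Consider hospitalization for subjects with CrCl <80mL/min at first dose of 20 mg and 50 mg".

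**The concern.** Two current texts in one appendix give different earliest times for relaxing a safety category in the same patients. If the general sentence governs, the 50 mg limit in the reassessment text does nothing. If the reassessment text governs, the general sentence is too broad for this group. Two sites could each follow the protocol and manage the same patient differently.

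What is at stake is the setting and the hydration at the first 20 mg and 50 mg doses. The limit in the reassessment text looks deliberate, because it falls just after the two doses for which hospital is recommended. Protocol section 1.6.3.1 describes the same practice in the venetoclax studies: patients with both features were admitted for the first day at 20 mg and at 50 mg.

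**Working it through.** No power or error rate is involved, so the check sets the texts side by side.

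**Timeline.** From section 3.7.5, 20 mg is given on days 1–7, 50 mg on days 8–14, and 100 mg from day 15. From section 3.6.4, randomization falls within 42 days of the screening tests and treatment starts within 14 days after that. The category assigned at screening can therefore be up to 42 + 14 = 56 days old at the first 20 mg dose. Appendix 6 (Laboratory Assessments) has a blood count with differential within 24 h before each ramp-up dose, so a newer ALC is at hand each time.

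**Who is affected.** All of the following must hold:
- ALC ≥25 × 10⁹/L at screening and a largest node of 5 to <10 cm. With a node ≥10 cm, the tables give high risk whatever the ALC.
- ALC below 25 × 10⁹/L before C1D1 or before day 8.
- CrCl above 50 mL/min, since 30–50 mL/min is handled as high risk anyway.

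**Worked case (illustrative values).** Node 6 cm, CrCl 90 mL/min, ALC 30 × 10⁹/L at screening, later 20 × 10⁹/L.

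| First dose of | General sentence, read literally | Reassessment text |
|---|---|---|
| 20 mg (day 1), if ALC is 20 before C1D1 | Medium: outpatient, extra IV fluid considered | High: hospital recommended, IV 150–200 mL/hr as tolerated |
| 50 mg (day 8), if ALC is 20 before day 8 | Medium: as above | High: as above |
| 100 mg (day 15) onward | Medium permitted | Medium permitted |

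The rules can differ at up to two dose steps and agree from the third. No study drug is given before C1D1, so a difference at 20 mg needs ALC to fall without treatment.

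**Post-dose chemistry at 20 mg and 50 mg.** The two risk lists and the prophylaxis table in Appendix 6 give 6–8 h and 24 h for medium and for high risk: 2 draws against 2, difference 0. Footnote 4 of the Appendix 1 schedule also makes no distinction by category: "6 h after ramp up dose of venetoclax and the day after (24 h) before next dose of venetoclax". Only the post-dose paragraph of Laboratory Assessments differs for high risk: "monitor blood chemistries in the hospital at 4, 8, 12 and 24 hours after initiating venetoclax at the 20 mg and 50 mg doses". On that paragraph alone the count is 4 against 2, difference 2.

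**Dose hold.** Both risk lists state that a patient with clinically significant electrolyte abnormalities "must have his or her subsequent venetoclax dose withheld until the electrolyte abnormalities resolve".

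**A related mismatch.** The reassessment text sets its node criterion at 5 cm or more with no upper limit. A patient with ALC ≥25 × 10⁹/L and a node ≥10 cm therefore falls under a rule that allows a move to medium risk, although the tables keep that patient high risk regardless of ALC.

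**The case against.** The best defence is that the texts do not strictly contradict each other. Both are permissive, and the reassessment text never says that earlier restaging is forbidden. Its only rule for keeping a patient at high risk depends on ALC, not dose. A sensible reader could take the general sentence as an overview that also serves patients moving from medium to low risk, and the later part as the specific rule for one subgroup. Clinical judgment governs in any case: Appendix 6 asks that comorbidities be considered before prophylaxis is settled and leaves hospitalization to the physician, and section 3.6.3 has the study office alert sites to patients at possible increased TLS risk.

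Much of this stands, and it keeps the point small. It does not remove it. The specific-over-general reading is plausible but written nowhere, and under the literal reading of the general sentence the 50 mg limit has no function.

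A reader might also infer that chemistry monitoring is lost when the category is lowered. The documents do not support that: only one paragraph gives high-risk patients extra draws, and it disagrees with the other places that set the schedule. Nor do they support reading the reassessment text as an outright ban that the general sentence breaks.

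**Conclusion.** The inconsistency is real and of minor severity. It is a drafting conflict in a safety rule, not a questionable design choice. Its effect is confined to the first 20 mg and 50 mg doses in the group defined above, and consists of a hospital recommendation and intravenous hydration giving way to outpatient dosing with extra fluid only considered. These are recommendations, not requirements.

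The number of patients affected is unknown and may be zero. The protocol does not give the share of patients with this combination of ALC and node size, or the share whose ALC falls in time. The synopsis expects a lower tumor burden than in other trials. Any count within the planned 25 treated patients would be a guess, so none is offered.

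A reader might infer that the trial's conclusions are at risk. They are not on this ground: the TLS category enters neither the definition nor the analysis of the primary endpoint, grade ≥3-infection-free survival at 24 weeks.

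**What to change.** In the general sentence under the risk table, drop the open-ended timing and add an exception along these lines: *except that patients who are high risk through ALC ≥25 × 10⁹/L and a largest node of 5 to <10 cm are restaged only as described under Reassessment of risk category (earliest before the 100 mg step); patients with any node ≥10 cm remain high risk regardless of ALC.* In the reassessment text, limit the node criterion to 5 to <10 cm so that it matches both tables. Restaging from medium to low risk and the CrCl 30–50 mL/min rule stay as they are.

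This adopts the stricter of the two readings, which fits the doses for which hospital is recommended; the sponsor should confirm that it is the intended one. The cost is a short amendment to Appendix 6. No new tests are needed, since the blood count before each ramp-up dose is already planned. The downside is that a few patients may have the first 20 mg dose, the first 50 mg dose, or both in the more intensive setting.

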1.6.3 Warnings and Precautions

1.6.3.1 Tumor Lysis Syndrome (TLS)

Tumor lysis syndrome, including fatal events, has occurred in patients with previously treated CLL with high tumor burden when treated with venetoclax.

Venetoclax can cause rapid reduction in tumor, and thus poses a risk for TLS in the initial 5 weeks dose titration phase. Changes in electrolytes consistent with TLS that require prompt management can occur as early as 6 to 8 hours following the first dose of venetoclax and at each dose increase.

The risk of TLS is a continuum based on multiple factors, including comorbidities. Patients with high tumor burden (e.g., any lymph node with a diameter ≥5 cm or high ALC ≥25 x 109/l) are at greater risk of TLS when initiating venetoclax. Reduced renal function (CrCl <80 ml/min) further increases the risk. Patients should be assessed for risk and should receive appropriate prophylaxis for TLS, including hydration and anti hyperuricaemics. Blood chemistries should be monitored, and abnormalities managed promptly. Dosing should be interrupted if needed. More intensive measures (intravenous hydration, frequent monitoring, hospitalization) should be employed as overall risk increases. The instructions for "Prevention of tumor lysis syndrome" should be followed.

Concomitant use of this medicinal product with strong or moderate CYP3A inhibitors increases venetoclax exposure and may increase the risk for TLS at initiation and during the dose-titration phase. Also inhibitors of P-gp or BCRP may increase venetoclax exposure. In the initial Phase 1 dose-finding studies, which had a shorter (2 to 3 week) titration phase and higher starting dose, the incidence of TLS was 13% (10/77; 5 laboratory TLS; 5 clinical TLS), including 2 fatal events and 3 events of acute renal failure, 1 requiring dialysis.

The risk of TLS was reduced after revision of the dosing regimen and modification to prophylaxis and monitoring measures. In venetoclax clinical studies, patients with any measurable lymph node \geq 10 cm or those with both an ALC \geq 25 x 10 9 /l and any measurable lymph node \geq 5 cm were hospitalized to enable more intensive hydration and monitoring for the first day of dosing at 20 mg and 50 mg during the titration phase.

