In 168 patients with CLL starting with a daily dose of 20 mg and increasing over 5 weeks to a daily dose of 400 mg in studies M13-982 and M14-032, the rate of TLS was 2%. All events were laboratory TLS (laboratory abnormalities that met \geq 2 of the following criteria within 24 hours of each other: potassium >6 mmol/l, uric acid >476 μ mol/l, calcium <1.75 mmol/l, or phosphorus >1.5 mmol/l; or were reported as TLS events) and occurred in patients who had a lymph node(s) \geq 5 cm or ALC \geq 25 x 10 9 /l. No TLS with clinical consequences such as acute renal failure, cardiac arrhythmias or sudden death and/or seizures was observed in these patients. All patients had CrCl \geq 50 ml/min.

In the open-label, randomized phase 3 study (MURANO), the incidence of TLS was 3% (6/194) in patients treated with venetoclax + rituximab. After 77/389 patients were enrolled in the study, the protocol was amended to incorporate the current TLS prophylaxis and monitoring measures described in Posology (see section 4.2). All events of TLS occurred during the venetoclax dosetitration phase and resolved within two days. All six patients completed the dose titration and reached the recommended daily dose of 400 mg of venetoclax. No clinical TLS was observed in patients who followed the current 5-week dose-titration schedule and TLS prophylaxis and monitoring measures (see section 4.2). The rates of grade ≥3 laboratory abnormalities relevant to TLS were hyperkalemia 1%, hyperphosphatemia 1%, and hyperuricemia 1%.

For details regarding risk factors, prophylactic measures and handling of TLS see appendix 6.

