3.7 STUDY DRUG

3.7.1 Premedications for Patients Randomized for Treatment

Due to risk of tumor lysis, all patients have to initiate allopurinol 300 mg once daily from one day prior to start on treatment until at least start of cycle 3; whether continuing allopurinol until end of cycle 3 is on the discretion of the treating physician. In the case of allergy to allopurinol, probenecid or rasburicase may be used as alternatives on the discretion of the treating physician. Sufficient oral hydration, at least 2 L per day, is required during venetoclax ramp up.

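### Appendix 6 makes uric-acid prophylaxis during the venetoclax ramp-up optional, although Section 3.7.1 and the appendix's own risk-group instructions require it

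*Protocol*

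**What the plan says.** The protocol states how long uric-acid prophylaxis lasts in four places.

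- **Section 3.7.1 (premedication):** "all patients have to initiate allopurinol 300 mg once daily from one day prior to start on treatment until at least start of cycle 3". The only duration left to the physician is whether to go on from there to the end of cycle 3. For allopurinol allergy, "probenecid or rasburicase may be used as alternatives on the discretion of the treating physician".
- **Appendix 6, low and medium risk patients:** an oral uric acid reducer, begun at least 24 hours before the first dose and "continued until at least 28 days after last dose escalation".
- **Appendix 6, high risk patients:** the same instruction in the same words.
- **Appendix 6, paragraph on anti-hyperuricemic agents, after the prophylaxis table:** "Start at least 1 day prior to initiation of venetoclax; consider continuing through the ramp-up phase".

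The prophylaxis table between the risk-group instructions and that paragraph gives a start but no duration. Its footnote b reads "Start allopurinol or xanthine oxidase inhibitor at least 1 day prior to initiation of venetoclax". Its high-risk row recommends rasburicase if baseline uric acid is raised, and adds "ALLOPURINOL SHOULD NOT BE GIVEN AT SAME DAY AS RASBURICASE".

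Section 1.6.3.1 directs the reader to this appendix: "For details regarding risk factors, prophylactic measures and handling of TLS see appendix 6".

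**The concern.** Three of the four statements set a minimum duration that covers the whole ramp-up and some weeks beyond it. The fourth asks the site only to think about continuing during the ramp-up. It does not refer back to the stricter text, and the protocol has no rule saying which wording prevails.

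The placing makes this worse. The table and its notes are the part of the appendix a site is likely to keep at hand, and the weak sentence is the only duration given there. The neighboring note on hydration covers the ramp-up phase without any such qualifier, so a reader could take the softer wording on uric acid as deliberate.

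The ramp-up is also when prophylaxis matters most. Section 1.6.3.1 places the TLS risk in the five-week titration and says that electrolyte changes "can occur as early as 6 to 8 hours following the first dose of venetoclax and at each dose increase". A site working from the table and its notes alone could stop the oral agent before a later increase and believe it was within protocol. These patients do not meet the criteria for CLL treatment, which is a further reason for the safety text to be unambiguous.

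**Working it through.** The protocol gives no day number for the end of prophylaxis, so there is no stated figure to reproduce. The check converts each rule to a study day on the uninterrupted schedule and then compares the four texts.

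**Inputs**

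- Venetoclax dose levels of 20, 50, 100, 200 and 400 mg, 7 days on each, starting on cycle 1 day 1 (Section 3.8; the table in Section 3.7.5 agrees).
- Cycles of 28 days (Section 3.8).
- Minimum A: start of cycle 3 (Section 3.7.1).
- Minimum B: 28 days after the last escalation (Appendix 6, both risk groups).

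**Dose increases**

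Level k starts on day 7 × (k − 1) + 1.

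| Level | Dose | Start day |
|---|---|---|
| 1 | 20 mg | 1 |
| 2 | 50 mg | 8 |
| 3 | 100 mg | 15 |
| 4 | 200 mg | 22 |
| 5 | 400 mg | 29 (cycle 2 day 1) |

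There are four increases after the first dose. The last is on day 29, and the five-week ramp-up ends on day 5 × 7 = 35.

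**Minimum duration under each rule**

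- A: cycle 3 day 1 = 2 × 28 + 1 = day 57.
- B: 29 + 28 = day 57.

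The two rules agree. Both run 57 − 35 = 22 days past the end of the ramp-up.

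**Side by side**

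| Text | Day 1 to 35 | After day 35, up to day 57 |
|---|---|---|
| Section 3.7.1 | required | required |
| Appendix 6, low/medium risk | required | required |
| Appendix 6, high risk | required | required |
| Appendix 6, anti-hyperuricemic paragraph | start required, continuation optional | not mentioned |

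The discretion also sits in a different place. Section 3.7.1 allows it only once cycle 3 has begun; the anti-hyperuricemic paragraph allows it while the dose is still rising. The increases on days 8, 15, 22 and 29 all fall in that window.

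**If the ramp-up is delayed**

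Suppose the last escalation slips by one week to day 36. Rule B then gives 36 + 28 = day 64. Rule A stays at day 57 if cycles are counted from cycle 1 day 1. Both are minimums, so the later one satisfies both. Wording tied to the last escalation therefore remains protective when doses are held.

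**The case against.** The best reply is that this is loose editing and the protocol already fixes the requirement. Section 3.7.1 is in the main body, applies to all treated patients and sets an unconditional minimum; a later suggestion to consider continuing cannot lower it. A site that stopped early because of the appendix paragraph would be in breach of Section 3.7.1. A reader who goes through Appendix 6 in order meets the 28-day rule as the first instruction for each risk group before reaching the weaker sentence, and the table is introduced as a summary. Other protections remain:

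- chemistry before each ramp-up dose and at 24 hours;
- withholding venetoclax when electrolytes are abnormal;
- hydration throughout the ramp-up;
- notice from the study office when a patient may be at increased TLS risk;
- an expected tumor burden lower than in other trial populations.

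Most of this stands. The texts can be met together, and harm would need a site to rely on one paragraph without the other three statements. It is also fair that only Section 3.7.1 uses the language of obligation; the risk-group instructions are directives with a minimum. These points limit the likely consequence, but the wording remains inconsistent. The paragraph reads as an operational instruction in its own right, and nothing tells a site to disregard it. The remaining checks detect or respond to tumor lysis; they do not replace the preventive agent.

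**Conclusion.** The concern holds. The anti-hyperuricemic paragraph in Appendix 6 makes optional what Section 3.7.1 and both risk-group instructions require. The required minimum is day 57, assuming an uninterrupted ramp-up and cycles counted from cycle 1 day 1. That day is derived here and is not printed in the protocol.

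The weaker wording covers four planned dose increases. It gives no stopping day, so no number of lost prophylaxis days can be stated, and the protocol offers no basis for estimating a change in TLS risk. The exposure is limited to a reader who uses this paragraph without the stricter texts. The point concerns safety and trial conduct; it touches neither the sample size nor the primary analysis. It should be corrected, but it is not a defect in the underlying design.

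**What to change.** In the anti-hyperuricemic paragraph of Appendix 6, delete the clause about considering continuation. In its place, instruct sites to continue the oral uric acid reducer (for example allopurinol) until at least 28 days after the last dose escalation, as stated above for each risk group.

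Leave the rasburicase provisions as they are in Section 3.7.1 and in the prophylaxis table, including the rule against giving it on the same day as allopurinol. Section 3.7.1 needs no change to remove the inconsistency.

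The cost is one clause in one appendix paragraph. It adds no visit or test, and no drug beyond what the protocol already requires.
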